Myxofibrosarcoma (MFS) represents one of the most common sarcomas in the adult / elderly age and its incidence is increasing due to the increase in the average age of the population; mainly affects the limbs and limbs, especially the lower limb. When compared to other histotypes, the typical feature of MFS is the tendency to a greater risk of local recurrence (RL) regardless of the degree of histological malignancy and surgical margins (60% vs. 25-30%)(1). Such local aggression could be caused by the specific histological pattern of infiltrative growth. Local recurrence is also characterized by a variable, but high (15–38%) progression of degree, thus increasing the metastatic potential at the time of any local relapse (2). The use of local (radiotherapy) or systemic (chemotherapy) adjuvant therapies have not shown efficacy in terms of increasing the control of local and / or systemic diffusion. Despite this, the prognosis of MFS is relatively good with a metastasis rate of 20-25% and an estimated survival of approximately 75% at 5 years and 70% at 10 years(3). Morphologically, it appears as a tumor with distinctive characteristics (association of hypocellular mixoid areas and hypercellular fibrous areas); however, it does not have a specific immunohistochemical pattern, so the histological diagnosis is mainly based on the hematoxylin-eosin morphology (4). MFS is characterized by nonspecific cytogenetic aberrations and complex and unbalanced karyotypes, which increase with increasing degree, suggesting a multi-step tumor progression process due to the acquisition of genetic instability (5). Recently, Heitze et al. in a series of 25 cases of MFS (grade 1 and 3) they identified some genes with amplified expression including CCND1, CCNE1, EGFR, PTEN, RET (MET) and some deleted genes including TP53 and RB1. The mutation analysis also highlighted the presence of somatic mutations in TP53, PTEN, FGFR3, CDKN2A, and RB1 (6).

However, for none of these alterations has a correlation been observed with the prognosis (in terms of overall or progression-free survival). On this basis, knowledge of genetic changes appears essential for the identification of potential biomarkers useful both at diagnostic / prognostic and therapeutic level.

OBJECTIVE OF THE STUDY

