The aim of the present study, in a serie of patients with a diagnosis of Mixofibrosarcoma treated at the Rizzoli Institute from *1 January 1993 up to 01 December 2017*, is to identify patients with different risk classes in terms of disease-free survival (local and systemic recurrence) and total survival. The study will exam all the clinical, radiological, histological and immunohistochemical features of this tumour in all samples and in a limited serie of cases the presence of mutation of 50 genes cancer related.

STUDY DESIGN

To identify patients with different risk classes in terms of disease-free survival (local and systemic recurrence) we will review about 200 cases of mixofibrosarcoma of extremities treated at our institution. We will perform immunohistochemical and molecular analysis by NGS, Sanger sequencing and Digital PCR considering 50 cancer-related genes. Survival analysis for disease free-survival and overall survival was carried out using Kaplan-Meier curves and log-rank tests.

POPULATION

Inclusion criteria

- 1) Male and female patients treated at Rizzoli Institute from 01 Jan 1993 to 01 Dec 2017
- 2) Diagnosis of mixofibrosarcoma of extremities
- 3) Histological slides/formalin-fixed paraffin-embedded tissue tumor (FFPE) blocks from archive available to perform the histology analysis and molecular analysis
- 4) Enough tumor biobanked material available for molecular analysis
- 5) Presence of the biobank signed informed consent
- 6) Written informed consent prior to any study-specific analysis and/or data collection

Exclusion criteria

- 1) Patients with histological diagnosis different from mixofibrosarcoma of extremities

MATERIAL AND METHODS

We will retrieve from the database of the Rizzoli institute all the cases with a histological diagnosis of mixofibrosarcoma of the extremities from 01 Jan 1993 to 01 Dec 2017

We aspect to find approximately 200 cases.

We will review all the medical records, radiological imaging, and histological data of these cases.

The immunohistochemical analysis of the principal altered genes identified in this tumor by the literature will be performed. In a limited serie of cases, we will perform NGS analysis of specific hot spot mutations cancer-related in 50 genes. Results obtained will be validated by Sanger sequencing and Digital-PCR in all the selected cases.

STATISTICS

To the case series will be applied a descriptive statistic.

DATA COLLECTION

Clinical data will be retrieved by patient charts.

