Human biological material (HBM) collection involves the collection and storage of biological material, residual biological material or derivatives in compliance with ethical and technical requirements.

Biological material (FFPE blocks and frozen tissue of tumor sample) are already stored in the archive of the Istituto Ortopedico Rizzoli, Pathology Department.

The biological material will be used and stored according with the sample characteristic and applicable regulation.

- The Istituto Ortopedico Rizzoli will have a designated person responsible for collection and will act as a communication point
- The collected HBM should be documented, i.e. the amount remaining and its location. act as a communication point

CONFIDENTIALITY

In order to ensure confidentiality of clinical trial data as disposed the national and European applicable regulation, data will be only accessible for the trial Sponsor and its designees, for monitoring/auditing procedures, the Investigator and collaborators, the Ethics Committee of each corresponding site and the Health Authority.

Investigator and the Institution will allow access to data and source documentation for monitoring, auditing, Ethic Committee revision and inspections of Health Authority, but

maintaining at all times subject personal data confidentiality as specified in the “Directive 95/46/EC of the European Parliament and of the Council of 24 October 1995”.

The Investigator must guarantee that patient anonymity is kept at all times and their identity must be protected from unauthorized persons and institutions.

All patients included in the study will be identified with a numeric code, so that no identifiable personal data will be collected (pseudo anonymization)

The Investigator must have and conserve a patients' inclusion registry where it figures the personal data of the patient: name, surname, address and corresponding identification code into the study, this register will be kept on the Investigator File.

PUBLICATION OF RESULTS

The results from this study will be published or shown at scientific conferences.

The final publication of the study results will be written by the Principal Investigator.

SPONSOR ROLE AND RESPONSIBILITY

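### Nothing in the protocol keeps those who score histology, immunohistochemistry and baseline imaging from knowing each patient's outcome

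*Protocol*

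**What the plan says.** The Objective of the Study "is to identify patients with different risk classes in terms of disease-free survival (local and systemic recurrence) and total survival". The predictors are broad: "The study will exam all the clinical, radiological, histological and immunohistochemical features of this tumour in all samples".

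The series is retrospective. Inclusion criterion 1 admits "Male and female patients treated at Rizzoli Institute from 01 Jan 1993 to 01 Dec 2017", so many outcomes are already on file, and the Informed Consent section expects that some eligible patients will have died. Criterion 3 requires slides or blocks "from archive available to perform the histology analysis and molecular analysis", so new histological work is planned.

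Material and Methods describes the review in one sentence: "We will review all the medical records, radiological imaging, and histological data of these cases". It then says that immunohistochemistry will be performed. Under Data Collection, "Clinical data will be retrieved by patient charts", and one case report form per subject records the results of the review.

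The opening background section says that the tumour lacks a specific immunohistochemical pattern, "so the histological diagnosis is mainly based on the hematoxylin-eosin morphology". The only exclusion criterion is a different histological diagnosis. Under Confidentiality, "All patients included in the study will be identified with a numeric code", and the investigator keeps the register that links code to patient.

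The protocol nowhere mentions masking of readers, independent or dual reading, or an order between scoring and outcome extraction.

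**The concern.** Reading morphology, staining and images takes judgement. In a prospective study the predictor is usually scored before the outcome exists. Here the outcomes largely exist already and sit in the charts that the team will review. A reader who knows that a patient relapsed can, without intent, resolve an equivocal field towards the worse category. That alone produces an association between feature and outcome where none exists, and it exaggerates a real one.

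The readings are the predictors from which the risk classes will be built, so this bears on the main aim. It is also a matter of study conduct rather than analysis: a statistical analysis plan cannot restore a score that was given with the outcome known. The safeguard has to be in place before the first reading.

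**Working it through.** **Is there a safeguard in the text?** Four places could provide one.

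- The review sentence in Material and Methods lists records, imaging and histology together and assigns no readers or order.
- Data Collection takes clinical data from the charts and says nothing about timing.
- The case report form is one per subject and is not split into readings and outcomes.
- The numeric code serves confidentiality. It is given to patients once included, and the investigator holds the key, so it does not in itself mask anyone.

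None of them separates scoring from outcome.

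**How large could the effect be?** The protocol gives no significance level, power or effect size, so it has no figure to reproduce. The following is an illustration.

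Inputs from the protocol: about 200 cases (expected archive count) and 60% local recurrence (background section, with no time point). Assumed: a binary feature with no true effect, read as high in about 40%; a two-sided 5% test; and a difference *d* in the frequency of high readings between relapsers and non-relapsers. The simulation also assumes that the 60% is reached at 5 years and that censoring falls at 4 to 6 years.

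Closed form, with 200 × 0.60 = 120 events:

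- P(high | relapse) = 0.40 + d/2; P(high | no relapse) = 0.40 − d/2
- share high: π = 0.6(0.40 + d/2) + 0.4(0.40 − d/2)
- relapse risk if high: r₁ = 0.6(0.40 + d/2)/π; if low: r₀ = 0.6(0.60 − d/2)/(1 − π)
- HR = ln(1 − r₁)/ln(1 − r₀)
- t = √(120 π(1 − π)) × ln HR; rejection rate = Φ(t − 1.96) + Φ(−t − 1.96)

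For d = 0.10: π = 0.27 + 0.14 = 0.41; r₁ = 0.27/0.41 = 0.659; r₀ = 0.33/0.59 = 0.559; HR = 1.0745/0.8194 = 1.31; t = 5.388 × 0.271 = 1.46; rejection rate = 0.31.

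The simulation draws survival times and fits a Cox model and a log-rank test. Separate runs of 2,000 and 4,000 replicates are shown as ranges.

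| d | Closed-form HR | Closed-form rejection | Simulated median HR | Simulated rejection |
|---|---|---|---|---|
| 0 | 1.00 | 5% | 1.00 | 5% |
| 0.05 | 1.15 | 11% | 1.12–1.14 | 10% |
| 0.10 | 1.31 | 31% | 1.28–1.30 | 27% |
| 0.15 | 1.50 | 59% | 1.45–1.46 | 53–54% |

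The closed form runs slightly high because it is an approximation. Both methods show the same pattern.

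**A different bias mechanism.** Now assume that half the tumours are truly high and that a share *f* of the low scores is raised, in patients with an event only. The same HR and rejection formulas apply. The protocol's 20–25% metastasis rate has midpoint 22.5%, so 200 × 0.225 = 45 events.

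| f | 45 events: HR, rejection | 120 events: HR, rejection |
|---|---|---|
| 10% | 1.19, 9% | 1.14, 11% |
| 20% | 1.43, 23% | 1.31, 31% |

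With masked reading d or f is zero, and both models return HR 1.00 and 5%.

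**The case against.** The strongest reply is that the protocol is silent rather than wrong. The review sentence is a list of sources. It does not say that one person sees both charts and slides, in what order, or whether images or only reports are consulted. Immunohistochemistry is new work and is not part of that sentence. Re-scoring of grade or margins is not announced; both appear only as background. All of this is correct, and a reader who infers that the protocol prescribes unmasked reading goes beyond the text. What stands is that the text permits such reading and contains nothing against it.

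A reader might also infer that known outcomes will decide who enters the cohort, since the diagnosis rests on morphology and a different diagnosis excludes. The documents do not support that as a stated procedure. Cases are retrieved by the diagnosis recorded in the database, and no step of diagnostic re-review is described. The risk arises only if the histology review leads to reclassification.

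It could be said that the reach is small. Sequencing and digital PCR calls leave little room for subjective scoring, the series is hypothesis-seeking, and the Statistics section promises only description. The first point stands. The others carry less weight, because the aim is to form risk classes and the Study Design names log-rank tests.

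Finally, the illustration shows what follows if bias is present. It is no evidence that bias will occur, and it models relapse but not death.

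**Conclusion.** The concern holds as a gap in study conduct. Judgement-based features are to be related to recurrence and survival in a series whose outcomes lie in the charts under review, and nothing prevents a reader from knowing the outcome when scoring. The harm would be irreversible once readings are made.

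Its size cannot be derived from the protocol. Under the assumptions above, a shift of 5 percentage points doubles the false-positive rate to about 10%, and a shift of 15 points brings it to about 53%, with a spurious hazard ratio of about 1.45. These results depend on the assumed shift, the 40% reading rate and the follow-up pattern.

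The point does not extend to a claim that scoring will be biased, that inclusion will depend on outcome, or that the existing numeric code already solves the problem. It is an inexpensive improvement that should be made before reading starts.

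**What to change.** Add to Material and Methods:

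- Baseline histology, immunohistochemistry and baseline (pre-treatment) imaging are scored under a study code assigned when the case is retrieved. The present code is given only to patients already included, which is too late to cover any diagnostic check.
- Readers are existing team members who do not handle chart abstraction, consent or the code register and who have no access to follow-up or later images. Consent matters here because whoever seeks it may learn that a patient has died.
- All scores, and any diagnostic reclassification, are locked before outcome data are linked.
- Cases whose reader already knows the outcome are flagged and left out in a sensitivity analysis.

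The cost is minor logistics: ordering the steps and dividing tasks among existing staff. No further patients or assays are needed.

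### Risk classes are to be identified and compared by log-rank in the same series of about 200 cases; if outcome guides how they are formed, the separation is expected to look too good, and no correction is named

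*Protocol*

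**What the plan says.** - **Aim** (Protocol, OBJECTIVE OF THE STUDY): the purpose "is to identify patients with different risk classes in terms of disease-free survival (local and systemic recurrence) and total survival". No class is defined beforehand, so the classes are something the study produces.
- **Candidates** (same section): "The study will exam all the clinical, radiological, histological and immunohistochemical features of this tumour in all samples". Gene mutations are looked for in only part of the series: "in a limited serie of cases the presence of mutation of 50 genes cancer related". The number of non-molecular features and the size of the sequenced subset are not given.
- **Material** (STUDY DESIGN; MATERIAL AND METHODS): "we will review about 200 cases of mixofibrosarcoma of extremities treated at our institution" and "We will retrieve from the database of the Rizzoli institute all the cases with a histological diagnosis of mixofibrosarcoma of the extremities". The archive is taken whole, with no part set aside. The count is an expectation: "We aspect to find approximately 200 cases".
- **Comparison** (STUDY DESIGN): "Survival analysis for disease free-survival and overall survival was carried out using Kaplan-Meier curves and log-rank tests". The STATISTICS section promises description only.
- **Validation** (MATERIAL AND METHODS): "Results obtained will be validated by Sanger sequencing and Digital-PCR in all the selected cases". This follows directly on the sequencing sentence and concerns mutation calls.

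**The concern.** A log-rank test keeps its nominal error rate when the groups are fixed without looking at survival. It loses that property when the groups were picked because survival differed between them in the same patients. The aim of identifying classes, the open list of candidates and the undivided series together make outcome-guided grouping a natural reading of the plan. Nothing named in the protocol would show how much of the resulting separation is real.

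At stake is the study's stated aim. Class curves that look well separated could be published and then fail in new patients. The protocol's introduction reports that none of the listed gene alterations has been found to correlate with prognosis, so a scenario with no true effect is a fair test case for the molecular features.

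**Working it through.** The protocol gives no alpha, power, effect size or event count, so there is no figure of its own to reproduce. The calculations below illustrate the mechanism.

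**Inputs from the protocol.** About 200 cases; 50 genes in a subset; two endpoints. The introduction gives local recurrence of 60% and survival of about 75% at 5 years and 70% at 10 years. Event shares of 25 to 60% are therefore a reasonable range.

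**Assumed inputs.** No true effect; independent binary features (prevalence 0.3 or 0.5 in step 2, 0.3 elsewhere); number of candidates; rule for forming classes; two-sided 0.05 level.

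**1. Single-feature tests.** The chance of at least one p<0.05 among m independent null tests is 1 − 0.95^m: 40% for m=10, 64% for m=20, 92% for m=50.

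**2. Classes from the best three features.** High risk means at least two of the three best-separating features; n=200; 2,000 null data sets per setting; hazard ratio estimated as exp[(O−E)/V].

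| Events | Candidates | Log-rank p<0.05 | Median apparent HR |
|---|---|---|---|
| 30% | 10 / 20 / 40 | 63 / 85 / 95% | 1.8 / 2.0 / 2.3 |
| 60% | 10 / 20 / 40 | 61 / 86 / 96% | 1.5 / 1.7 / 1.8 |

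Repeat runs gave 61-65, 85-87 and 95-97%, with median hazard ratios of 1.5 to 2.4.

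**3. A different class rule.** A signed score of the three strongest features, cut near its median, at 25, 45 and 60% events (500 to 1,000 runs per setting), gives p<0.05 in 54-61% (10 candidates), 78-82% (20) and 92-95% (50). Median apparent hazard ratios are 1.6-2.1, 1.8-2.5 and 2.0-3.1. The same classes applied to fresh patients reject in 3.7-6.4% of runs, with a median hazard ratio of 0.98-1.04. The excess therefore comes from re-using the data.

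**4. Sequenced subset.** With an assumed 60 cases and 50 genes, the rule in step 3 gives p<0.05 in 92-96% of runs and median apparent hazard ratios of 3.9-8.5. A prevalence of 0.3 for every gene is generous; fewer informative genes would lower these figures.

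**5. One continuous marker with a searched cut-point.** p<0.05 in 34-37% of runs (n=200).

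**6. Effect of a corrected screen.** With a Bonferroni screen of 20 features, the chance of selecting any under the null is 1 − (1 − 0.05/20)^20 = 4.9%. The estimate is still inflated when something passes. A two-sided threshold of 0.0025 needs |Z| of at least 3.02. With V ≈ d × 0.3 × 0.7:
- 30% events: d = 60, V = 12.6, so the apparent hazard ratio is at least exp(3.02/√12.6) ≈ 2.3.
- 60% events: d = 120, V = 25.2, so it is at least exp(3.02/√25.2) ≈ 1.8.

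A null or weak feature can pass only by showing an effect of at least that size (or its reciprocal).

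**7. Would a split sample serve?** Schoenfeld's formula with equal classes and a true hazard ratio of 2.0 gives power of 69% at 50 events and 41% at 25 (25% events, whole series against half). At 120 and 60 events (60%) it gives 97% and 77%. Splitting is costly; resampling keeps every patient.

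**The case against.** The strongest reply is that the class-building step is inferred. The protocol states no score, selection rule, cut-point search or model. Identifying classes could mean no more than survival curves by grade, margin or mutation status, and such groups are defined without reference to outcome. Each log-rank test would then be valid at its own level, with only multiplicity left. This stands, and it is why the point is conditional.

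Second, the class rule and any resampling could sit in a statistical analysis plan that is not shown. This also stands, so the point rests only on what the protocol fixes: one undivided series used both for identification and comparison, and validation confined to the assay. No sentence rules resampling out.

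A reader might infer four stronger things that the documents do not support:
- That the reported separation is certainly over-optimistic and every log-rank test invalid. That would require an outcome-driven rule, which the protocol does not state.
- That the high false-positive rates persist after multiplicity correction. Step 6 shows that they fall to about 5%; only the inflation of a selected effect remains.
- That the Sanger and digital PCR sentence is wrong, or is offered as prognostic validation. It is neither; it is an accurate description of a laboratory check.
- That a hazard ratio is the study's main output. The protocol names none; it is used here only to measure separation.

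**Conclusion.** The point holds in conditional form. To the extent that outcome in this series guides the choice of features, cut-points or groupings, the final class comparison is expected to overstate separation, and the protocol names nothing that would correct it. Under unadjusted selection of the best three among 10, 20 or 40 features with no true effect, nominal significance would arise in about 60-65, 85 and 95% of studies, with median apparent hazard ratios of about 1.5 to 2.4. The direction follows from the design. The size cannot be computed from the protocol: the number of candidates, class rule, prevalence, independence of features and subset size are assumed, and the event shares are only bracketed by the introduction. The bias would be absent if all classes were fixed before outcomes were examined.

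**What to change.** In STUDY DESIGN and STATISTICS:
- State that any class derived from outcome in this series is exploratory.
- Repeat the entire class-building process (feature choice, cut-points, grouping) within bootstrap samples or cross-validation.
- Report optimism-corrected discrimination (C-index) and optimism-corrected survival differences between classes, for both disease-free and overall survival.
- Do not present the log-rank p-value between derived classes as confirmatory.
- Allow groups fixed in advance without reference to outcome, such as grade or margin, to keep their log-rank tests.

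The sequencing sentence can stay as it is. No new patients are needed. The costs are some programming, the need to write the class-building rule down so that it can be repeated (including how genes unmeasured outside the subset are handled), and a reported separation that will look less favourable.

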A protocol-specific CRF reporting the results of the review will be provided.

A CRF is required and should be completed for each included subject.

ETHICS AND QUALITY ASSURANCE

The clinical trial protocol and its documents will be sent before initiating the study to the competent Authorities and Ethics Committees of each participating country for its approval.

The responsible investigator will ensure that this study is conducted in agreement with either the most updated Declaration of Helsinki and all the international and local laws that apply to clinical trials and to patient protection.

The protocol has been written, and the study will be conducted according to the principles of the ICH Harmonized Tripartite Guideline for Good Clinical Practice

(ref: <http://www.emea.eu.int/pdfs/human/ich/013595en.pdf>).

INFORMED CONSENT

All patients will be informed, by the investigator, of the aims of the study, the possible risks and benefits that will derive from the study participation.

The Investigator must clearly inform that the patient is free to refuse participation in the study and that can withdraw consent at any time and for any reason.

They will be informed as to the strict confidentiality of their patient data, but that their medical records may be reviewed for trial purposes by authorized individuals other than their treating physician.

The informed consent procedure must conform to the ICH guidelines on Good Clinical Practice. This implies that "the written informed consent form should be signed and personally dated by the patient or by the patient's legally acceptable representative".

The Investigator must also sign the Informed Consent form, and will keep the original at the site and a copy of the original must be handed to the patient.

The competent ethics committee for each Institution participating to the study must validate local informed consent documents before the study can be opened. It will be emphasized that the participation is voluntary and that the patient is allowed to refuse further participation in the study whenever he/she wants. This will not prejudice the patient's subsequent care.

Due to the high incidence of mortality of the disease under investigation, it would be possible that some potential eligible subjects will be deceased.

GENERAL PRINCIPLES FOR HUMAN BIOLOGICAL MATERIAL (HBM) COLLECTION

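### The STATISTICS section omits the log-rank tests named in STUDY DESIGN, and one-feature log-rank tests neither estimate effects nor combine features into the risk classes the study aims to identify

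*Protocol*

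**What the plan says.** OBJECTIVE OF THE STUDY says the aim "is to identify patients with different risk classes in terms of disease-free survival (local and systemic recurrence) and total survival". On the material to be used it says: "The study will exam all the clinical, radiological, histological and immunohistochemical features of this tumour in all samples". A 50-gene mutation analysis is added in a limited subset.

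STUDY DESIGN repeats the aim for disease-free survival, states that "we will review about 200 cases of mixofibrosarcoma of extremities", and closes with the analysis: "Survival analysis for disease free-survival and overall survival was carried out using Kaplan-Meier curves and log-rank tests".

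STATISTICS reads in full: "To the case series will be applied a descriptive statistic". It mentions no survival analysis and no test.

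The protocol does not say which features define the groups to be compared. It names no model, score or other rule that turns several features into a risk class.

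**The concern.** There are two linked problems.

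- **The sections do not match.** Kaplan-Meier curves can fairly be called descriptive, but a log-rank test is a hypothesis test. An analyst working from STATISTICS would run no test; one working from STUDY DESIGN would. The past tense, in a plan otherwise written in the future, leaves unclear whether that sentence describes planned or finished work.
- **The named methods do not deliver the aim.** Descriptive summaries form no classes. A log-rank test compares groups that are already defined, whereas here the classes are what the study must find. Applied to each feature in turn, it gives a p-value per feature, with no estimate of how strongly the feature bears on outcome and no means of combining features.

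At stake is the study's only stated aim. The work could end with a list of separate comparisons and no defined risk classes.

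**Working it through.** The protocol gives no alpha, power, effect size, event count or follow-up length, so there is no stated figure to reproduce. The check is mainly textual, with arithmetic to show what the named test leaves unreported.

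**1. Aim against method**

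| Needed for the aim | Descriptive statistic | Kaplan-Meier and log-rank, one feature at a time |
|---|---|---|
| Compare survival between levels of a feature | Curves only | Yes |
| Size of effect with an interval | No | Not from the test |
| Combine several features | No | No |
| Place each patient in one class | No | No; each feature gives its own split |

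The last row matters most. A patient can be on the favourable side of one feature and the unfavourable side of another. Separate tests give overlapping splits and do not say in which class that patient belongs.

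**2. Events available**

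Inputs: about 200 cases (STUDY DESIGN), and from the background section an "estimated survival of approximately 75% at 5 years and 70% at 10 years".

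Expected deaths by year 10, if all 200 are analysed and followed that long: 200 × (1 − 0.70) = 60.

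This figure is conditional. Censoring before year 10 would lower it, and so would a smaller analysed series. Inclusion requires "Written informed consent prior to any study-specific analysis and/or data collection", while INFORMED CONSENT concedes that "it would be possible that some potential eligible subjects will be deceased". Deaths after year 10 would add to it, since the protocol sets no 10-year limit.

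**3. What a log-rank p-value leaves unsaid**

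For a yes/no feature present in a fraction q of cases, with D deaths, the standard error of the log hazard ratio is about 1/√(D·q·(1 − q)). At two-sided p = 0.05 the hazard ratio is exp(1.96/√(D·q·(1 − q))). The lower 95% limit is then 1.00 and the upper limit is the square of the estimate. With D = 60:

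- Feature split 50:50: D·q·(1 − q) = 60 × 0.5 × 0.5 = 15; exp(1.96/√15) = exp(0.506) = 1.66; upper limit 1.66² = 2.75.
- Feature split 20:80: 60 × 0.2 × 0.8 = 9.6; exp(1.96/√9.6) = exp(0.633) = 1.88; upper limit 1.88² = 3.54 (from the unrounded estimate).

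The splits are assumed for illustration. The same p-value goes with different effects, and both intervals run from no effect to a large one. The test alone reports neither estimate nor interval.

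**4. Why classes formed from a model need a caution**

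This is an illustration under assumed inputs: 200 cases; survival matched to the two background figures; censoring uniform from 1 to 26 years, cut at 10 years (about 54 deaths); and features with no effect at all. A Cox score was fitted, cut into thirds, and tested by log-rank in the same data. The test was significant at 5% in about 44-45% of simulated studies with six features and about 15-17% with three. Thirds are only an example of a rule.

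**The case against.** The strongest reply is that the sections do not truly conflict. STATISTICS is incomplete rather than opposed, and the natural reading is descriptive summaries plus the survival comparison already named. That stands. A reader might infer that nobody can tell which analysis governs, but the text does not support so strong a claim for a single-centre archive review whose endpoints and survival methods are both named.

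A second reply is that grouping variables, cut-offs and the classification rule commonly sit in an SAP, which may exist. This stands in part: absence of that detail is not the finding. The finding is that the methods the protocol does name cannot produce classes from several features, and nothing in it points to one that can.

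A third is that the aim allows a looser reading: find the single features whose levels separate survival. Feature-by-feature tests would serve that. The protocol does not say it means this, but the possibility is why the aim *may not* be met, rather than cannot be. Simpler rules, such as counting adverse features, would also form classes; none is stated.

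A reader might also infer that unadjusted marker results will be confounded by grade. The documents do not support this. The background ties grade to karyotype complexity, not to the immunohistochemical markers or the 50 genes. A marker linked to outcome through grade would show a true unadjusted association, and value beyond grade is not a stated aim.

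**Conclusion.** The concern holds in a limited form. STATISTICS omits the inferential test that STUDY DESIGN names, the latter is in the wrong tense, and one-feature log-rank tests yield neither effect sizes nor a way to combine features into risk classes. The study's only stated aim may therefore not be met by the plan as written.

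The point should be fixed but is not fatal, because it can be corrected without new data. The text comparison needs no assumption. The figure of about 60 deaths assumes all 200 cases are followed to year 10 with 70% survival, and the hazard ratios of 1.66 and 1.88 assume that count and the stated splits. They illustrate what goes unreported; they are not a claim about power.

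**What to change.** Put one survival analysis in STATISTICS, in the future tense, and have STUDY DESIGN refer to it. For example:

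> Features will be summarised descriptively. Kaplan-Meier curves and log-rank tests will give unadjusted comparisons. For each of disease-free and overall survival, a multivariable Cox model of prespecified features, including grade, will be fitted and hazard ratios reported with 95% confidence intervals. Risk classes will be formed from this model by a rule fixed before the analysis. P-values across classes derived in the same data are descriptive.

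Keep the number of model parameters modest relative to the events; for overall survival the guide is about 60 deaths by year 10, fewer if not all 200 cases are analysed. The covariate list, cut-points and validation may sit in the SAP, with a cross-reference. The Cox model is one suitable choice; what matters is that a method able to combine features is named.

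The cost is a few sentences of protocol text and modest extra analysis on data already being collected. There are two downsides: fewer features are likely to appear significant, and classes fitted and assessed in the same data will look better than they are. The second is the reason for the descriptive label.
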